#### 5 STATISTICAL CONSIDERATIONS

# 5.1 General Principles

Descriptive statistics (mean, median, standard deviation, minimum, and maximum) will be summarize continuous variables, Frequencies and percentages will be used to summarize categorical variables. The two-sided 95% exact confidence interval using Clopper-Pearson methodology (Clopper 1934) will be calculated for the response rates where applicable (e.g., ORR).

The median survival time will be estimated using the Kaplan-Meier method; the associated 95% confidence interval (CI) will be calculated based on the complementary log-log transformation (Collett 1994).

Unless otherwise specified, data are to be summarized by dose level and overall. DLT analysis will only include patients in Part A and Part C dose finding part.

Any analysis not described in this plan will be considered exploratory, and will be documented in the clinical study report (CSR) as a post hoc analysis or a change to the planned analysis.

To comply with regulatory electronic submission guidelines, listings of all clinical data will be submitted as electronic data sets. To facilitate data review for the study report, only pertinent data listings will be created and attached to the appendix of the CSR. All statistical tables, listings, and figures will be produced using SAS, version 9.3 or more recent. Other statistical software, if used, will be described in the CSR.

#### 5.2 Determination of Sample Size

Approximately 189–211 patients will be enrolled in this study, of which approximately 12–24 patients will be enrolled in Part A, approximately 73 patients will be enrolled in Part B (approximately 48 in Cohort 1 and approximately 25 in Cohort 2), and approximately 64 enrolled in Part C, and approximately 40 patients will be enrolled in Part D.

#### 5.2.1 Part A

Part A will start with 6 patients at 2.5 mg/kg, capped at 80 kg prior to Amendment 2 or 100 kg under Amendment 2 and later. If 2 or more patients experience a DLT, the dose level will be de-escalated to 2.0 mg/kg, capped at 80 kg prior to Amendment 2 or 100 kg for patients treated under Amendment 2 and later. If there are <2 patients experiencing DLTs, the dose level will be expanded to a total of 12 patients. If 4 or more patients experience a DLT among the 12 patients, the dose level will be de-escalated to 2.0 mg/kg, as described above. If <4 patients experience a DLT among the 12 patients, Part B Cohort 1 of the study may be initiated at 2.5 mg/kg, capped as described above.

If the dose level is reduced to 2.0 mg/kg, this dose level will initially enroll 6 patients and the same dose de-escalation algorithm will be used. If further de-escalation is needed, the dose level will be determined by the sponsor in consultation with the SMC.

Study SGNLVA-002 Ladiratuzumab vedotin Statistical Analysis Plan Seagen, Inc. - Confidential

01-May-2024 Page 10 of 32 If the true incidence rate of DLT is 10%, the probability of de-escalation to 2.0 mg/kg is 12%. The probability of de-escalation increases to 96% if the true incidence rate of DLT is 50%.

#### 5.2.2 Part B

Once the MAD has been identified in Part A, Patients will be enrolled in Part B Cohort 1 at the MAD. Approximately 42 LIV-1-positive patients in total will be enrolled at the MAD. Based on the SGNLVA-001 phase 1 study, it is estimated that about 70% of patients are LIV-1-positive. Approximately 60 patients are expected to be enrolled at the MAD, assuming that Part A will enroll 12 patients at the MAD and approximately 48 patients are expected to be enrolled in Part B Cohort 1 at the MAD. Assuming the observed ORR is between 50% and 70%, the widths of 2-sided 95% confidence intervals (CIs) are summarized as below.

Confirmed ORR	Expected width of 95% CI on LIV-1- positive patients (N=42)	Expected width of 95% CI on all patients at the MAD(N=60)
50%	±16%	±13%
60%	±16%	±13%
70%	±15%	±12%

Part B Cohort 2 will enroll approximately 25 patients at 2.0 mg/kg. With the patients in Part A enrolled at 2.0 mg/kg, approximately 30 patients in total will be enrolled at 2.0 mg/kg. Assuming the observed ORR is between 50% to 70%, the widths of 2-sided 95% CIs are summarized as below.

Confirmed ORR	Expected width of 95% CI on all patients at 2.0 mg/kg (N=30)
50%	±18%
60%	±18%
70%	±16%

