The safety analysis set will include patients treated with any amount of LV or pembrolizumab. This is also referred to as the all treated patients set for some efficacy analyses. The DLT-evaluable (DE) analysis set includes all patients in the safety analysis set who either (1) experience a DLT or (2) receive at least 75% of intended LV and pembrolizumab doses and are followed for the full DLT evaluation period (Cycle 1). The DE patient set will be the primary population for Part A, and will be used for the determination of the MAD for Part B. The all treated analysis set includes all enrolled patients who receive any amount of LV or pembrolizumab and will be the primary set for efficacy analysis. The efficacy-evaluable (EE) set includes all patients in the all treated analysis set who have both a baseline and at least 1 evaluable post-baseline disease assessment according to the RECIST v1.1 and iRECIST criteria, or per investigator determination of clinical disease progression.

Exact 95% confidence intervals (CIs) for ORR and DCR will be provided. DOR, PFS, and OS will be analyzed using the Kaplan-Meier method. The primary analyses of efficacy endpoints will be performed for all treated patients analysis set. All safety analyses will be based on the safety analysis set.

Approximately 60 patients total are expected to be enrolled at the MAD assuming that Part A will enroll 12 patients at the MAD and Part B Cohort 1 will enroll approximately 48 patients, at the MAD. Based on the SGNLVA-001 Phase 1 study, it is estimated that about 70% of patients are LIV-1-positive. Thus, approximately 42 LIV-1-positive patients in total will be enrolled at the MAD. Assuming the observed ORR is between 50% and 70%, the widths of 2-sided 95% CIs are summarized below.

Confirmed ORR	Expected width of 95% CI on LIV-1-positive patients (N=42)	Expected width of 95% CI on all patients at the MAD (N=60)
50%	±16%	±13%
60%	±16%	±13%
70%	±15%	±12%

Part B Cohort 2 will enroll approximately 25 patients at 2.0 mg/kg. With the patients in Part A enrolled at 2.0 mg/kg, approximately 30 patients in total will be enrolled at 2.0 mg/kg. Assuming the observed ORR is between 50-70%, the widths of 2-sided 95% CIs are summarized as below.

	Expected width of 95% CI on all patients at 2.0 mg/kg		
Confirmed ORR	(N=30)		
50%	±18%		
60%	±18%		
70%	±16%		

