9.3.1. General Considerations

In general, descriptive statistics will be presented that include the number of observations, mean, median, standard deviation, minimum and maximum for continuous variables, and the number and percentages (of non-missing) per category for categorical variables.

The 2-sided 95% exact CI using Clopper-Pearson method (Clopper 1934) will be calculated for the response rates where applicable (e.g., ORR).

For time-to-event endpoints, the median survival time will be estimated using the Kaplan-Meier method; the associated 95% CI will be calculated based on the complementary log-log transformation (Collett 1994).

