# 6.6.1 Efficacy Endpoints

# 6.6.1.1 Objective Response Rate (ORR)

ORR is defined as the proportion of patients with confirmed CR or PR according to RECIST Version 1.1. Patients who do not have at least 2 (initial response and confirmation scan) postbaseline response assessments will be counted as non-responders.

The observed ORR and the 95% confidence intervals will be provided using Clopper-Pearson methodology.

The maximum percent reduction (or minimum percent increase if there is no reduction) in the sums of diameters from baseline will be derived for each patient and will be graphically displayed (e.g., using a waterfall plot).

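### The precision quoted for 2.0 mg/kg (N=30) comes from the normal approximation, so it is slightly better than the planned Clopper-Pearson interval will deliver

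*SAP*

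**What the plan says.** SAP 5.2.2 adds the Part A patients treated at 2.0 mg/kg to the roughly 25 of Part B Cohort 2, so that "approximately 30 patients in total will be enrolled at 2.0 mg/kg". For observed response rates of 50%, 60% and 70%, "the widths of 2-sided 95% CIs are summarized as below": ±18%, ±18% and ±16%. The column is headed "Expected width of 95% CI on all patients at 2.0 mg/kg (N=30". No interval method is named for this table. Protocol 9.1.2 and the synopsis (Statistical Methods) repeat it with the same figures.

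The analysis method is named elsewhere. SAP 5.1 states: "The two-sided 95% exact confidence interval using Clopper-Pearson methodology (Clopper 1934) will be calculated for the response rates". SAP 6.6.1.1 says of the primary endpoint: "The observed ORR and the 95% confidence intervals will be provided using Clopper-Pearson methodology". Protocol 9.3.1 and 9.3.6.1 specify the same method. Neither document plans any other interval for ORR.

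The companion table in SAP 5.2.2 gives ±16/±16/±15% for 42 LIV-1-positive patients and ±13/±13/±12% for 60 patients at the MAD. The Part C (N=62) and Part D (N=40) tables are labelled exact and print the limits themselves.

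**The concern.** A precision table should describe the interval that will be reported. If the N=30 figures come from a different and narrower interval, the plan promises more precision at 2.0 mg/kg than the analysis will give. The reader is not told that the method has changed from the table just above it. This is also the only statistical statement of what about 30 patients at 2.0 mg/kg provide, so nothing else in the plan corrects it.

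A second issue is the ± format. Away from 50% the Clopper-Pearson interval is asymmetric, with its longer arm on the low side for rates above 50%. That is the side that matters when judging whether activity is maintained at the lower dose.

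**Working it through.** **Inputs.** Two-sided 95% level, N=30, and observed rates of 50%, 60% and 70% (SAP 5.2.2), which are 15, 18 and 21 responders. Planned method: Clopper-Pearson (SAP 5.1 and 6.6.1.1; protocol 9.3.1 and 9.3.6.1).

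**Reproducing the printed figures.** The Wald half-width is 1.96 × √(p(1−p)/30):

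- 50%: 1.96 × √(0.25/30) = 17.89 points
- 60%: 1.96 × √(0.24/30) = 17.53 points
- 70%: 1.96 × √(0.21/30) = 16.40 points

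These round to 18/18/16 and match all three cells. Wilson, Agresti-Coull, Jeffreys, mid-P, continuity-corrected Wald and Clopper-Pearson averaged over the binomial distribution were also tried. None matches all three.

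**The planned interval.** For x responders of n, the lower limit is the 2.5% quantile of Beta(x, n−x+1) and the upper limit is the 97.5% quantile of Beta(x+1, n−x).

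| Responders | Printed | Wald half-width | Clopper-Pearson limits | Half-width | Lower arm |
|---|---|---|---|---|---|
| 15/30 (50%) | ±18% | 17.89 | 31.3% to 68.7% | 18.70 | 18.7 |
| 18/30 (60%) | ±18% | 17.53 | 40.6% to 77.3% | 18.37 | 19.4 |
| 21/30 (70%) | ±16% | 16.40 | 50.6% to 85.3% | 17.33 | 19.4 |

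The exact half-widths round to 19/18/17.

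**Lower limits, Wald against exact.** 32.1% against 31.3% (0.8 points), 42.5% against 40.6% (1.9 points) and 53.6% against 50.6% (3.0 points). The 3.0 points at 70% have two parts:

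- half-width: 17.33 − 16.40 = 0.93
- asymmetry: the exact interval is centred on (50.60 + 85.27)/2 = 67.94, which is 2.06 below 70

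**The other tables.** These show which method the plan normally uses.

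| N | Printed | Clopper-Pearson half-width | Wald half-width |
|---|---|---|---|
| 42 | 16/16/15 | 15.8/15.5/14.7 | 15.1/14.8/13.9 (rounds to 15/15/14) |
| 60 | 13/13/12 | 13.2/13.0/12.2 | 12.7/12.4/11.6 (rounds to 13/12/12) |

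For N=42 the 60% and 70% rows use 25 and 29 responders, the nearest whole numbers. Both columns fit Clopper-Pearson and not Wald. The N=62 and N=40 limits also reproduce as Clopper-Pearson.

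**Does an approximate N explain it?** Clopper-Pearson half-widths were computed for each N from 28 to 37, taking x = N × rate. None rounds to 18/18/16. The nearest are N=31 to 33 (18/18/17) and N=34 (17.6/17.3/16.3, so 18/17/16).

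**The case against.** The case against giving this much weight is fair on most counts:

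- **Size.** The half-widths differ by 0.8 to 0.9 points, and the 60% cell does not change after rounding.
- **The 3-point figure.** The table prints no limits, and about 2 of the 3 points at 70% come from the ± format. A corrected ±17% would still suggest 53% against an exact 51%. The N=60 column has the same weakness: 70% ± 12% suggests 58% against an exact 56.8%.
- **Consequence.** SAP 5.7 rules out formal hypothesis testing, no go/no-go rule uses these widths, and the reported interval will be Clopper-Pearson in any case.
- **N is loose.** The Part A algorithm enrols 6 or 12 patients at 2.0 mg/kg if that level is completed, giving 31 to 37 with Cohort 2. At N=31 only the 70% cell would be wrong.
- **Purpose and timing.** Protocol 3.2.3.1 justifies Cohort 2 mainly on tolerability, and the SAP dates from May 2024, so a correction cannot affect enrolment.

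All of this limits the importance of the point, but none of it makes the table right. The heading says N=30, the figures are not those of the planned method at N=30, and no nearby N restores them. The format objection supports printing limits rather than half-widths.

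**Conclusion.** The N=30 table is wrong as written. It shows Wald half-widths where the plan specifies Clopper-Pearson, and it is the only ORR precision table to do so. On the planned method ±18/±18/±16% becomes ±19/±18/±17%. The lower limit at 70% is 50.6%, which is 3.0 points below the unrounded Wald limit of 53.6% and 3.4 points below the 54% implied by the printed ±16%.

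The error flatters precision at the lower dose, and it understates the loss relative to the 2.5 mg/kg group. At 70% the printed half-widths differ by 16 − 12 = 4 points; the exact ones differ by 17.33 − 12.18 = 5.15.

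The practical effect is small and confined to the description of the design. The result assumes exactly 30 patients and whole-number responder counts. That the printed figures are Wald is inferred from the match, because the documents name no method for this table.

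**What to change.** Replace the N=30 table in SAP 5.2.2, protocol 9.1.2 and the synopsis with exact limits in the format already used for Parts C and D:

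| Confirmed responses | Confirmed ORR | 95% exact CI (N=30) |
|---|---|---|
| 15 | 50% | 31%, 69% |
| 18 | 60% | 41%, 77% |
| 21 | 70% | 51%, 85% |

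The N=42 and N=60 columns are correct as half-widths. Giving them as limits too would be tidy but is not needed.

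The cost is three rows in three places and a slightly less favourable statement of precision. Sample size, conduct and analysis are unchanged. If the protocol is not otherwise being amended, correct the SAP and note the difference in the clinical study report.

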#### 5.2.3 Part C

In Part C, it is estimated that approximately 4 to 12 patients (assuming evaluation of 2 dose levels) will be treated in dose escalation. Operating characteristics of the dose escalation design, including the average number of patients allocated to each dose across a variety of toxicity scenarios, are presented in the simulation report (Error! Reference source not found.).

Up to approximately 64 patients may be enrolled across the dose escalation and expansion cohorts in Part C. In the case that both dose levels go to expansion, approximately 12 patients will be enrolled in each dose level (assuming 2 patients in each of the dose escalation cohort of 1.0 and 1.25 mg/kg and 60 patients in the expansion cohort).

The table below summarizes the 2-sided 95% exact confidence intervals among 62 patients at 1.25 mg/kg (2 in dose escalation and 60 in dose expansion cohort) assuming the observed ORR is between 50% and 70%.

Study SGNLVA-002 Ladiratuzumab vedotin Statistical Analysis Plan Seagen, Inc. - Confidential 01-May-2024 Page 11 of 32

Number of confirmed Objective Response	Confirmed ORR	95% exact CI (N=62)	
31	50%	37%, 63%	
37	60%	46%, 72%	
43	69%	56%, 80%	

#### 5.2.4 Part D

Approximately 40 patients will be enrolled in Part D. Ongoing, real-time, continuous review of patient safety and SAEs will be conducted by the sponsor's Drug Safety Department. Additionally, the ISMC will ensure periodic safety data review throughout the study.

Presented in the table below are the 2-sided 95% exact CIs among 40 patients at 1.5 mg/kg assuming the observed ORR is between 50% and 70%.

Number of confirmed Objective Responses	Confirmed ORR(%)	95% exact CI (N=40)
20	50%	34%, 66%
24	60%	43%, 75%
28	70%	53%, 83%

This sample size of 40 patients would additionally provide the following probabilities of observing at least 1 patient having an AE, as summarized below.

True AE Incidence Rate	Probability of Observing at Least One Patient Having an AE (N=40)
5%	87%
10%	99%

# 5.3 Randomization and Blinding

This is a single-arm, open-label study. No randomization will be utilized.

#### 5.4 Data Transformations and Derivations

#### 5.4.1 General

Reported age in years will be used; if not available, age in years will be calculated with the SAS INTCK function (with method specified as "continuous") using informed consent date and birth date.

Study SGNLVA-002 Ladiratuzumab vedotin Statistical Analysis Plan Seagen, Inc. - Confidential 01-May-2024 Page 12 of 32 Study Day will be calculated as Date – First Dose Date + 1 for dates on or after the first dose date. For dates prior to the first dose date, Study Day will be calculated as Date – First Dose Date. For all calculations of Study Day, the First Dose Date will be the earliest date of treatment administration for SGN-LIV1A or pembrolizumab.

Other time variables based on two dates, e.g., Start Date and End Date, will be calculated as (End Date – Start Date + 1) (in days) unless otherwise specified in the planned analysis section.

The following unit conversion will be implemented unless otherwise specified:

$$Months = Days / 30.4375$$

$$Years = Days / 365.25$$

Unless otherwise specified, baseline values used in all analyses will be the most recent nonmissing measurement prior to the first dose of study drug.

The end-of-treatment (EOT) date will be the date the EOT visit is performed; if an EOT visit is not performed then the EOT date will be either the EOS date or 30 days after the last dose of any study drug, whichever is earlier.

# 5.4.2 Response Assessment Dates

At each response assessment time point, scans to evaluate target and non-target lesions can be performed on multiple dates. If the time point response is CR or partial response (PR), then the latest date of all radiologic scans at the given response assessment visit will be the date of response. If the time point response is stable disease (SD), then the earliest date of all radiologic scans at the given response assessment visit will be the date of SD. If the time point response is PD, then the earliest date that PD has been documented will be the date of PD, i.e. the earliest of:

- Date of target lesion assessments when the target lesion response is PD
- · Date of non-target lesion assessments when the lesion status is unequivocal progression
- Date of documenting new lesions

#### 5.4.3 Best Response

Primary analysis of response will be based on RECIST Version 1.1.

A patient's best response will be the best demonstrated response to date that has been confirmed. Confirmation is required for PR and CR only. Once a patient achieves a confirmed PR, only evidence of CR will potentially change the patient's confirmed best response. The patient's best response will be used in determining the ORR.

Study SGNLVA-002 Ladiratuzumab vedotin Statistical Analysis Plan Seagen, Inc. - Confidential 01-May-2024 Page 13 of 32 Per RECIST Version 1.1, a response (CR or PR) will be considered confirmed if the following disease assessment (at least 4 weeks after the initial response) still shows response (CR or PR). A patient will have a best response of SD if there is at least one SD assessment (or better) >5 weeks after the start of treatment and the patient does not qualify for CR or PR. The details of best response are provided in 0 and Appendix E.

# 5.5 Handling of Dropouts and Missing Data

With the exception of the scenarios covered in this section, missing data will not be imputed.

Patients who do not have at least two (initial response and confirmation scan) post-baseline response assessments will be counted as non-responders for analysis of the primary endpoint.

AE dates will be imputed for the purpose of calculating duration of events and treatment-emergent status (see Appendix AAppendix A for imputation details and Appendix B Imputation of Partial Missing Prior Therapy Dates

When calculating time since most recent prior therapy, please following the following algorithm.

The most recent prior therapy date is defined as the latest among all the prior therapies including therapy start and end date. And if prior therapies date are partially missing, please following the following imputation rule. Prior therapy dates will be imputed if both month and year are present and only day is missing.

- For prior therapy start date, impute the first day of the month.
- For prior therapy end date, impute the last day of the month or 1 day before the first dose of study drug, whichever is earlier.

Appendix C for the treatment-emergent definition). Censoring will be described in Section 6 with each planned analysis, as applicable.

Unless otherwise specified, lab values which are recorded or provided as being less than the lower limit of quantification (LLOQ), will be included in figures and summaries as LLOQ/2. For the purpose of grading, lab values reported as less than LLOQ will be imputed as LLOQ.

#### 5.6 Multicenter Studies

There are multiple centers in this study, however it is not anticipated that any center will accrue enough patients to warrant an analysis by center.

# 5.7 Multiple Comparison/Multiplicity

No multiple comparisons are planned, and no formal hypothesis testing will be performed.

# 5.8 Examination of Subgroups

As exploratory analyses, subgroup analyses may be conducted for selected endpoints. Subgroups may include but are not limited to the following:

PD-L1 expression

#### 5.9 Covariates

No adjustment for covariates is planned in the analyses.

# 5.10 Timing of Analyses

The primary analysis will be conducted when all treated patients have come off study. Subsequent cutoff dates may be defined and corresponding database locks may occur to allow for more precise estimates of time-to-event endpoints.

### 6 PLANNED ANALYSES

# 6.1 Disposition

Patient disposition will be summarized for all enrolled subjects with descriptive statistics. Patients who discontinue study treatment and patients who withdraw from the study will be summarized along with reason for discontinuation or withdrawal. The number of patients in each analysis set will be summarized. The reasons for screen failure will also be described, if applicable. The number of patients enrolled at each site will be summarized.

## 6.2 Demographic and Baseline Characteristics

Demographics and baseline characteristics, including age, sex, ethnicity, race, baseline height, weight, and ECOG score will be listed and summarized; summaries will be presented using All Treated analysis set. Disease specific characteristics will also be listed and summarized All Treated analysis set.

Study SGNLVA-002 Ladiratuzumab vedotin Statistical Analysis Plan Seagen, Inc. - Confidential 01-May-2024 Page 16 of 32

#### 6.3 Protocol Deviations

Important protocol deviations (defined as protocol violations by Seagen) are those that represent a divergence from the protocol that could have a significant effect on the integrity of the study data, or on the subject's rights, safety, or welfare. Important protocol deviations also include exemptions to the study inclusion/exclusion criteria and will be summarized by category.

